### **Microscopic Colitis**

Physician's global assessment and number of unformed bowel movements per 24 hours were employed to assess response to FMT as these parameters used to determine MC treatment in clinical trials and care.

### **Irritable Bowel Syndrome**

The Irritable Bowel Syndrome Symptom Severity Scale (IBS-SSS) is a validated instrument with a scoring system which produces a meaningful value that is both reproducible and sensitive to change. The instrument contains five questions across the following domains: pain; distension; bowel score and quality of life. Each question can generate a maximum score of 100 using prompted visual analogue scales; the maximum achievable score is 500. IBS-SSS is mild for scores 75 – 175; moderate 176 – 300 and severe if > 300.

## **The Proposed Trial**

### **The proposed design of the study**

The design of this research is a prospective open-label trial using lyophilized or frozen FMT to evaluate efficacy of fecal microbiota transplantation for treatment of chronic gastrointestinal (GI) dysbiosis and clearance of antimicrobial resistant organism (ARO) from the GI tract of the ARO colonized individuals.

### **The planned trial interventions**

#### **Recruitment**

The research coordinator will be responsible for coordinating the recruitment, screening of potential participants using the inclusion/exclusion criteria and reviewing with the PI. The PI will make the final determination of a potential participants' eligibility. Fifty participants with chronic GI dysbiosis will be recruited. Twenty patients with confirmed ARO will be recruited to take part in this study; the ARO study results will be used to determine the feasibility of further study.

#### **Study Population**

The participants will consist of patients over the age of 18 years who or their legally authorized representative consent and comply with study procedures. Participants will be required to have a formal diagnosis of chronic gastrointestinal dysbiosis by a referring gastroenterologist or known to be colonized with ARO based on positive rectal cultures for same organism on 2 separate occasions (each culture 1 month apart) and must have a positive culture within 14 days of enrollment.

#### **ARO Participants**

Following informed consent and prior to receiving FMT, enrolled ARO participants will have their blood collected for Hepatitis BsAg, Hepatitis C Ab, HIV, Syphilis serologies. Blood is collected for these pathogens to determine their serostatus at the time of study enrollment. Participants are advised through the study consent that if their blood tests positive for any of these diseases, the researchers are required to notify the public health department and that the public health department may contact them.

At baseline, ARO participants will have medical history, physical exam done by the physician-researcher, and information on concomitant medications will be collected. The participants will receive a total of two lyophilized FMT (LYO-FMT) or frozen FMT enemas using stool samples collected from healthy, screened donor(s); the participant will receive the first FMT treatment week 1 and a second FMT will be administered within three weeks of first treatment. Participant's stool will be retested one week, one month and 3 months following the second FMT to determine whether the ARO has been eradicated.

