### **Primary Outcome Measurements:**

For the participants with chronic GI dysbiosis, the efficacy of FMT treatment will be based on improvement in participant's symptom score from baseline (pre-transplant) to intervention (post-transplant) 4 weeks, 12 weeks and 1 year following FMT. For participants with ARO colonization, determination of clearance of ARO based on stool culture for ARO at baseline, day 7, day 30 and 3 months following last FMT.

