## GI Dysbiosis Participants

Following informed consent and pre-transplant, enrolled participants will have their blood collected for Hepatitis BsAg, Hepatitis C Ab, HIV, Syphilis serologies unless these serologies were performed within 3 months of enrollment. Blood is collected for these pathogens to determine their serostatus at the time of study enrollment and prior to receiving FMT.

All participants will be assessed at day 1 by the physician-investigator. A medical history and physical examination will be performed. In addition, optional blood and stool samples may be collected from IBD/IBS participants who consented for these samples prior to the FMT and at weeks 4, 12 and 6 months from FMT.

The participants will receive lyophilized FMT (LYO-FMT) or frozen FMT enemas using stool collected from healthy, screened donor(s). Participants will receive FMT treatment via retention enema(s) twice weekly for 4 weeks. If there is symptom improvement after 4 weeks of treatment, then the participants will receive FMT treatment once weekly for 4 additional weeks. If the participant does not experience symptom improvement after the initial 4 weeks of treatment, the physician-investigator will discuss options with the participant and a mutual decision will be reached to pursue an additional 4 weeks of FMT treatment or withdraw from the study and pursue usual care. When continued improvement is seen then the participants will receive FMT maintenance; the frequency of FMT treatment is participant dependent and is at the discretion of the physician-investigator and is based upon clinical exam and symptomatic improvement. If no improvement is seen after the 8th FMT, then the participant will be withdrawn from the study and s/he reverts to usual care for his/her condition. Participants can opt to receive maintenance FMT in the clinic or be trained by study staff for home administration.

At the time of each study visit and follow up, participants will be assessed for clinical response, including bowel movements and adverse reactions. Any participant who reports worsening symptoms or AE/SAE will return to the clinic for assessment by the physician investigator. At that time, the participant will undergo a physical exam. Additional tests may be ordered (i.e. blood work) at the discretion of the treating physician investigator.

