#### **Participant exclusion criteria**

- Planned or actively taking another investigational product
- Patients with neutropenia with absolute neutrophil count  $<0.5 \times 10^9/L$
- Evidence of toxic megacolon or gastrointestinal perforation on abdominal x-ray
- Peripheral white blood cell count  $> 30.0 \times 10^9/L$  AND temperature  $> 38.0^{\circ}C$
- Active gastroenteritis due to *Salmonella*, *Shigella*, shiga toxin-producing *E. coli*, *Yersinia* or *Campylobacter*.
- Unable to tolerate FMT or enema for any reason.
- Requiring systemic antibiotic therapy at the time of FMT.
- Actively taking *Saccharomyces boulardii* or other probiotic; yogurt is allowed
- Severe underlying disease such that the patient is not expected to survive for at least 30 days.
- History of severe allergy to any food

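### The plan provides no record of other therapy, or of changes in it, for dysbiosis participants, so improvement due to other treatment cannot be told apart from response to FMT

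*Combined protocol and SAP*

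**What the plan says.** The protocol describes its two cohorts in parallel sections. Under ARO Participants, the baseline entry lists history and examination and adds that "information on concomitant medications will be collected".

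Under GI Dysbiosis Participants, the day-1 entry is: "A medical history and physical examination will be performed". Serologies and optional samples are also listed. For later visits the text is that "participants will be assessed for clinical response, including bowel movements and adverse reactions". Medication is not named at either point.

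The primary outcome for the dysbiosis cohort is "improvement in participant's symptom score from baseline (pre-transplant) to intervention (post-transplant) 4 weeks, 12 weeks and 1 year following FMT". The design is a "prospective open-label trial using lyophilized or frozen FMT", and no control arm is described.

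The participant exclusion criteria bear on other treatment in three places: "Planned or actively taking another investigational product", "Requiring systemic antibiotic therapy at the time of FMT", and current use of probiotics. The statistical analysis section names logistic regression and survival methods for response and failure. It gives no covariates and no rule for a participant whose other treatment changes.

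**The concern.** Symptom scores in ulcerative colitis, Crohn's disease, microscopic colitis and IBS respond to drugs other than FMT. The protocol's own background says that current drug treatments can reduce symptoms in ulcerative colitis, and that budesonide may work in the short term in microscopic colitis. In a randomised trial, a concurrent control arm would show how much improvement arises under other care. Here nothing does: the whole within-person change is read as the effect of FMT.

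Over follow-up of up to 1 year, a participant may start, increase, reduce or stop conventional therapy. If the change is not recorded, the analyst cannot reclassify that participant, adjust for the change, or even report how many were affected. The loss is hard to repair after the data are in.

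**Working it through.** **Step 1. The two cohorts side by side.**

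| Item | ARO cohort | Dysbiosis cohort |
|---|---|---|
| Outcome | Stool culture | Symptom score |
| History and examination at entry | Yes | Yes |
| Concomitant medication at entry | Named, separately from history | Not named |
| Medication changes in follow-up | Not named | Not named |
| Longest primary assessment | 3 months | 1 year |

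The cohort whose outcome is a symptom score, followed for longest, has no stated medication record. The ARO record is for baseline only, so copying that sentence across would not supply follow-up data.

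**Step 2. Whether another section fills the gap.** The exclusion criteria cover investigational products, probiotics, and systemic antibiotics around FMT. They do not address conventional therapy for the conditions under study. The only drug use inside a score is the opiate item of the CDAI, which applies to Crohn's disease alone. The analysis section is silent. No section fills the gap.

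**Step 3. The plan's figures.** The sample size section gives 5% response on placebo, 24% on FMT, 5% significance, 80% power and 50 participants. With a two-sided test and unpooled variance:

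(1.960 + 0.842)² × (0.05 × 0.95 + 0.24 × 0.76) / 0.19² = 49.98, so 50.

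This is a per-arm size for a two-arm comparison, whereas the plan uses it as the total of an uncontrolled cohort. That is a separate matter. Here the 5% and 24% serve only as reference rates.

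**Step 4. Illustration of size.** Let r be the true response to FMT and c the share of would-be non-responders who improve because of other therapy while still being assessed. The documents give no value for c; the range below is an assumption.

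Apparent response = r + (1 − r) × c

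| c | r = 5% | Extra responders in 50 | r = 24% | Extra responders in 50 |
|---|---|---|---|---|
| 0 | 5.0% | 0 | 24.0% | 0 |
| 5% | 9.8% | 2.4 | 27.8% | 1.9 |
| 10% | 14.5% | 4.8 | 31.6% | 3.8 |
| 15% | 19.3% | 7.1 | 35.4% | 5.7 |
| 20% | 24.0% | 9.5 | 39.2% | 7.6 |

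For c = 10% and r = 5%: 0.05 + 0.95 × 0.10 = 0.145.

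**Step 5. The opposite direction.** Let d be the share of would-be responders who lose their response because other therapy was reduced or stopped. With c = 0, apparent response = r × (1 − d). For r = 24% and an assumed d = 10%, this is 0.24 × 0.90 = 21.6%. With unrecorded changes of both kinds, the sign of the net bias is not known.

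**The case against.** Three objections carry weight.

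- **Silence is not proof of absence.** A reader might infer that medication is not collected at all in the dysbiosis cohort. The documents do not support that. A day-1 history by the physician-investigator may well capture current drugs, applying the exclusion criteria means asking about some of them, and the study's data-capture forms are not part of the documents. What stands is narrower: the protocol does not provide for the record, and a day-1 history cannot show what changes afterwards.
- **Withdrawal limits exposure.** Participants without improvement may leave for usual care after 4 weeks, and those with none after the 8th FMT are withdrawn. Many of those likeliest to need more treatment would go early. This makes large values of c less plausible. It does not remove the problem for partial improvers, for those who continue by mutual decision, or for those on maintenance up to 1 year, some of them treated at home.
- **The bias need not run one way.** A reader might infer that the response rate can only be inflated. Participants may also taper or stop drugs while on FMT. The background section reports symptomatic relapse in up to 80% of microscopic colitis patients after budesonide is stopped. Such changes would lower the apparent response.

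A reader might also infer from the last row of the table that other therapy alone could produce the planned 24%. That needs c = 20%, for which the documents give no support. The 24% is also stated without an assessment time and comes from a trial in ulcerative colitis, not from this mixed cohort.

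**Conclusion.** The gap is real and worth closing before more data are collected. As written, the plan has no stated means of identifying dysbiosis participants whose other therapy changed, and no rule for analysing them. In an uncontrolled open-label study with a symptom outcome, improvement after added therapy in those who remain would count as FMT response.

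The size is unknown. It depends on how often therapy changes among participants still under assessment, which the documents do not say, and on how far withdrawal removes those most affected. The move from 5% to 14.5% shows sensitivity under one assumed value and is not an estimate. The plan states no success criterion, so the bias cannot be turned into a false-positive rate without a further assumption. The direction is upwards for starts and increases, and may be downwards for reductions and stops.

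**What to change.** **Data collection (GI Dysbiosis Participants section).** Record concomitant disease-directed medication at day 1. Record any start, increase, reduction or stop at each assessment: 4 weeks, 12 weeks and 1 year. For participants on home maintenance, obtain this by contact. If the forms already collect it, the protocol need only say so.

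**Analysis (statistical analysis section).** List disease-directed therapy by condition, so that minor symptomatic drugs do not become failures by default. Prespecify an analysis in which a participant who started or increased such therapy before an assessment counts as a non-responder at that assessment. Report response and score change with and without participants whose therapy changed in either direction. Because the non-responder rule does not deal with reductions, the second comparison is needed as well. It selects on an event after baseline, so it should be read as a sensitivity analysis.

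**Cost.** A short medication form at each assessment, the work of drawing up the lists, contact with home-maintenance participants, and a possibly lower reported response rate. The change concerns recording and analysis only; it prescribes no treatment.

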Microscopic colitis (MC) is a chronic inflammatory disease of the colon as manifested by chronic, watery, non-bloody diarrhea. MC usually occurs in middle-aged individuals with a female preponderance. Currently, there are limited treatment options for MC; budesonide may be effective for short-term treatment of MC and can improve quality of life. However, up to 80% will experience symptomatic relapse following cessation of budesonide. Routine maintenance treatment with budesonide is controversial as long-term treatment may increase the risk of steroid-related side effects.

IBS is characterized by chronic, relapsing abdominal discomfort and altered bowel movements – constipation, diarrhea or mixed (diarrhea and constipation). IBS affects approximately 15-20% of Canadians and its economic and social burden is estimated to be over \$6.5 billion per year in healthcare costs, work productivity losses, and reduced quality of life (QoL). The etiology and pathophysiology of IBS are not yet established, but appear to be a complex interplay between the host and environment factors. Currently, there are no evidence-based therapies available to cure IBS. Studies have shown that fecal microbiota transplantation (FMT) may be an effective IBS treatment. Given the lack of safe and effective treatment for IBD and IBS which are thought to be due to gastronintestinal dysbiosis, this study was conducted.

There is also some evidence in the literature showing efficacy of FMT in clearance of antimicrobial resistant organism (ARO) such as extended-spectrum of beta-lactamases (ESBLs), carbapenem resistant or vancomycin resistant enterococci from the gastronintestinal tract of colonized patients. There have been requests from clinicians to utlize FMT for eradication of ARO in rectally colonized patients admitted to an acute care facility in order to facilitate their discharge to a longterm care facility as they were otherwise eligible to be transferred.

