### **Proposed sample size and the justification for the assumptions**

Fifty participants will be recruited for the chronic GI dysbiosis component of the study based on the 5% response in placebo group and 24% in FMT arm with significance level 5% and power of 80% in the FMT trial of ulcerative colitis. For the ARO participants, the sample size will be 20 as this will be a pilot project to determine the feasibility of further study.

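### For ARO participants the plan describes no record of systemic antibiotics after baseline and no rule for cultures taken on them, so a culture-only clearance result cannot be separated from an antibiotic effect

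*Combined protocol and SAP*

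**What the plan says.** All references are to the combined protocol and SAP.

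- **Outcome.** *Primary Outcome Measurements* defines the ARO outcome as "determination of clearance of ARO based on stool culture for ARO at baseline, day 7, day 30 and 3 months following last FMT". *ARO Participants* gives the same schedule: "Participant's stool will be retested one week, one month and 3 months following the second FMT to determine whether the ARO has been eradicated". Neither section makes the result conditional on antibiotic exposure, and neither says whether clearance needs one negative culture or all of them.
- **Antibiotic rule.** *Participant exclusion criteria* lists "Requiring systemic antibiotic therapy at the time of FMT". This is the only antibiotic rule for participants.
- **Medication record.** *ARO Participants* states: "At baseline, ARO participants will have medical history, physical exam done by the physician-researcher, and information on concomitant medications will be collected". No later collection is described.
- **Treatment.** Two enemas are given; "a second FMT will be administered within three weeks of first treatment".
- **Design and size.** "The design of this research is a prospective open-label trial using lyophilized or frozen FMT", with no comparator described. "For the ARO participants, the sample size will be 20 as this will be a pilot project to determine the feasibility of further study".
- **Analysis.** The statistical analysis section names a binary response analysis, logistic regression and survival methods. It has no rule for a culture taken on antibiotics.

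**The concern.** The second study objective is the efficacy of FMT for clearing the resistant organism. The evidence for it is a short series of cultures over 3 months. An antibiotic active against the organism can turn a culture negative while the participant is still colonized. A later course could also disturb the flora and work against clearance. A control arm would show how often cultures convert for reasons other than FMT, but none is described. That leaves exposure dates as the only means of telling an antibiotic effect from an FMT effect, and the plan does not ask for them. Once follow-up is over, an analyst cannot reliably rebuild them.

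The protocol treats antibiotics as relevant to the gut flora elsewhere. *Study Rationale and Background* counts antibiotic history among the grounds for suspecting an altered microbiota, and *Donor exclusion* bars donors with antibiotic use in the 3 months before donation. For recipients, no record is described over the 3 months in which the outcome is read.

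What is at stake is the decision on further study, which the protocol says the ARO results will inform.

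**Working it through.** **1. Where could an antibiotic course after FMT be recorded or handled?**

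| Section | What it covers | Closes the gap? |
|---|---|---|
| *Participant exclusion criteria* | Antibiotic need when FMT is given | No. Even if applied at both enemas, it ends with the second |
| *ARO Participants* | Medications at baseline; stool retests afterwards | No |
| *GI Dysbiosis Participants* | Clinical response, bowel movements and adverse reactions at visits | No. Written for the other group, and medications are not listed |
| *Adverse Event Reporting* | Events, in the study file and REDCap | Not reliably. Treatments given for events are not mentioned |
| Statistical analysis and frequency of analyses | Methods and timing | No handling rule |

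**2. Is there a planned figure to reproduce?** No. The ARO sample size of 20 is a pilot number, given without alpha, power or an expected clearance rate.

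**3. Weight of one participant.** 1/20 = 5 percentage points.

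**4. Illustration of size.** Let p be true clearance, a the share of participants on an active antibiotic at the culture that decides the result, and s the chance that the antibiotic makes a still-colonized participant culture-negative. The documents give none of these, so all three are assumptions.

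Apparent clearance = p + (1 - p) × a × s

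Expected false clearances in 20 = 20 × (1 - p) × a × s

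With p = 0.30:

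| a | s | Apparent clearance | False clearances in 20 |
|---|---|---|---|
| 0.10 | 0.25 | 0.30 + 0.70 × 0.10 × 0.25 = 0.3175 (32%) | 0.35 (about 0.4) |
| 0.20 | 0.50 | 0.30 + 0.70 × 0.20 × 0.50 = 0.37 (37%) | 1.4 |
| 0.30 | 1.00 | 0.30 + 0.70 × 0.30 × 1.00 = 0.51 (51%) | 4.2 |

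Over the same ranges of a and s, apparent clearance is 22% to 44% if p = 0.20 and 42% to 58% if p = 0.40.

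The chance of at least one false clearance is 1 - (1 - (1 - p) × a × s)^20. With p = 0.30 it runs from 1 - 0.9825^20 = 0.30 to 1 - 0.79^20 = 0.99.

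**5. Dependence on the clearance rule.** Step 4 treats the result as resting on a single culture. If every culture had to be negative, one suppressed culture would do no harm so long as another was positive, and the numbers would fall. If any one negative culture were enough, each culture would be a further chance of error, and they would rise. The plan does not say which rule applies.

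**6. Scale against sampling error.** For 6 of 20 cleared (30%), the exact (Clopper-Pearson) 95% interval is 12% to 54%. It covers chance variation only and would not show a shift caused by antibiotics.

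**7. Direction.** The formula covers false clearance only. Failures caused by a later course would pull the estimate the other way. The documents give nothing from which to size that.

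**The case against.** Several points on the other side stand.

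- **Silence is not proof of absence.** A reader might infer that later antibiotics go unrecorded. The documents only fail to describe a record. An infection that needed treatment might surface through adverse event tracking, but nothing requires the drug and dates or links them to the endpoint.
- **The plan does not say that a suppressed culture counts as eradication by FMT.** That reading is tempting, but the clearance rule is undefined. What can be said is that such a culture would be read like any other.
- **The ARO group is not defined as acute-care inpatients.** The background reports that "There have been requests from clinicians to utlize FMT for eradication of ARO in rectally colonized patients admitted to an acute care facility", but eligibility is not limited to inpatients. The same sentence describes those patients as otherwise ready for transfer to long-term care. Later antibiotic use is plausible; its frequency is unknown.
- **A bias of 5 to 25 points is not supported.** It can be reached by assuming that 20-50% receive some antibiotic during follow-up and that a quarter to half of those yield a suppressed culture (1 to 5 of 20). The documents give neither rate. A false clearance also needs a course close to a culture, a drug active against an organism enrolled because it is resistant, and a participant still colonized.
- **The bias need not favour FMT.** It could run either way. The background's remark on antibiotics concerns dysbiosis and says nothing about losing ARO clearance.
- **This is a 20-patient pilot without a control.** The interval is wide, and spontaneous clearance would remain a rival explanation even with a perfect log.

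These points limit the size and certainty of the concern. They do not supply the missing record or the missing rule, and clearance is still the primary outcome for this group.

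**Conclusion.** The concern holds in a limited form. The documents describe no recording of systemic antibiotics after baseline for ARO participants, no rule for cultures taken on or soon after a course, and no comparator. The planned data therefore cannot separate an antibiotic effect, in either direction, from an FMT effect. The certain part of the size is 5 points per misclassified participant. The range of about 0.4 to 4.2 false clearances in 20 rests on assumed values throughout, on a result decided by one culture, and at its top end on 30% exposure with complete suppression. It shows that the problem could matter; it does not estimate a bias. The change should be made, because it is cheap and cannot be made well after follow-up has ended. It does not invalidate the pilot.

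**What to change.** 1. Record every systemic antibiotic (drug, start date, stop date) from enrolment to the 3-month culture, asked at the planned stool collections.
2. Prespecify that any culture, negative or positive, taken during a systemic antibiotic or within a stated window afterwards is non-evaluable for the primary clearance call. The call then rests on the remaining scheduled cultures. No culture is scheduled after 3 months, so a participant whose 3-month culture is affected is reported as indeterminate at that time point. The documents give no basis for the length of the window; the sponsor should choose and justify it before analysis.
3. In the same endpoint text, state whether clearance needs one negative culture or all of them.
4. Report clearance for all participants as the main figure, with a sensitivity analysis by antibiotic exposure after FMT. Exposure arises after treatment, so the subgroup figures are descriptive.

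**Cost.** A one-page log and a short addition to the endpoint definition. The protocol describes the follow-up contacts as stool retests, so a few questions must be added to them. A few cultures will become non-evaluable, and the reported clearance rate may be lower. Antibiotic use for clinical need is unchanged. Spontaneous clearance remains an uncontrolled rival explanation and should be named as such in the report.
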